6.2.1 Rationale for Exploratory Immunological Assessments

[Redacted]

[Redacted]

[Redacted]

[Redacted]

[Redacted]

[Redacted]

6.3 Risk/Benefit Assessment

Antibodies against both full-length Rib and Alpha proteins, [REDACTED] as well as antibodies reactive with the GBS-NN vaccine candidate, naturally occur in women exposed to GBS, and such antibodies are efficiently transferred to the unborn child *in-utero*. Many adults and new-born infants have, therefore, already been naturally exposed to both the proteins from which the antigen is derived and to antibodies against these proteins, and no side effects have been attributed as a consequence of such exposure in humans.

The planned excipients in the vaccine formulation are also all well-known from other vaccines, and no novel or non-tested components are used. The vaccine is adsorbed with a known adjuvant, Alhydrogel, (0.5 mg of Al³⁺ per dose), corresponding to the dose used in many other commercial vaccines. Volunteers will receive maximum of 2 dosing occasions in the clinic. The initial Phase I trial will include up to 310 healthy adult women using contraceptives – Part A enrolling up to 70 women and Part B enrolling up to 240 women. The vaccine will be given by the intramuscular route as was done in the animal safety studies. The Phase I trial will evaluate ascending dose levels of GBS-NN with and without Alhydrogel®.

A number of preclinical studies have been conducted in rats, rabbits and mini pigs. [REDACTED]

Initial safety and immunogenicity evaluation of escalating dose levels will select an appropriate dose for further evaluation in the target population of pregnant women to investigate if immunisation of pregnant women with GBS-NN can result in detectable IgG antibodies in the neonate that might provide protection to the new-born infants. [REDACTED]

[REDACTED] Thus doses of 10µg, 50µg and 250µg to be used in the present study will remain within the safety margins, and no overdosage is expected.

The normal adverse event profiles from Phase I studies suggest that a typical array of minor clinical study symptoms may be experienced by volunteers taking part in the study. GBS-NN has not previously been tested in human volunteers, although it is known that naturally occurring antibodies, reactive against the GBS-NN are found in pregnant women; the possibility of as yet unknown side effects should remain a consideration. The protocol requires that volunteers are monitored after vaccine administration (vital signs and general signs and symptoms), with regular follow-up visits for physician assessment and questioning regarding AEs will be conducted for all volunteers in the study. GBS-NN, like other protein-based vaccines, may theoretically be associated with a transient febrile reaction (body temperature greater than 38.0°C but not greater than 38.7°C) following vaccination. Immune complex-mediated reactions are unlikely given the recombinant nature of GBS-NN, however, it is still possible that hypersensitivity may occur.

Based on the results from clinical use of other protein vaccines adsorbed to Alhydrogel®, and other aluminium containing adjuvants transient local reactions at the injection site, including pain, oedema, bruising, erythema and induration, mainly of mild intensity, are likely to occur. In addition flu-like symptoms, such as fatigue, malaise, myalgia, and mild to moderate headache may occur.

GBS-NN vaccination is contraindicated in volunteers known to suffer hypersensitivity reactions to vaccines or a known allergy to aluminium hydroxide. For the purpose of the study volunteers who have experienced a significant illness in the four weeks prior to check in will be excluded. The vaccine should not be given to volunteers with known or suspected immune deficiency, autoimmune diseases or who have an acute infection.

GBS-NN should not currently be given to women known, or suspected to be, pregnant, or to nursing mothers. Currently GBS-NN should only be administered to women of child-bearing potential if adequate contraceptive precautions are taken, accompanied by serum and/or urine pregnancy testing prior to vaccination and during follow up.

All study volunteers will be monitored for potential side effects of vaccination during the entire course of the study, as per the protocol, and adverse events must be appropriately followed up.

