9. STUDY POPULATION

9.1 Inclusion Criteria

1. Healthy adult female volunteers (as determined by medical history, physical examination, laboratory test values, vital signs and electrocardiograms [ECGs] at screening) aged 18 – 40 years.
2. Body mass index (BMI) ≥ 18 and ≤ 30 kg/m².
3. Volunteers weight ≥ 50 kg and ≤ 100 kg at screening.
4. Able to voluntarily provide written informed consent to participate in the study.
5. Must understand the purposes and risks of the study and agree to follow the restrictions and schedule of procedures as defined in the protocol.
6. Volunteers must be pre-menopausal. Volunteers who have had a hysterectomy will have pre-menopausal status confirmed by a FSH and oestradiol test.
7. Females of childbearing potential must have a negative pregnancy test at screening (β HCG) and prior to each dose and must be willing to use an adequate and highly effective method of contraception until at least Day 85 of the study. A highly effective method of birth control is defined as one which results in a low failure rate (i.e. less than 1% per year) when used consistently and correctly such as sterilisation, implants, injectables, combined oral contraceptives, IUDs (Intrauterine Device), condoms, occlusive caps (cervical/vault caps) with spermicidal foam/gel/ film/cream/suppository. True sexual abstinence is acceptable when this is in line with the preferred and usual lifestyle of the volunteer (periodic abstinence e.g. calendar, ovulation, symptothermal, post-ovulation methods, declaration of abstinence for the duration of the trial, and withdrawal are not acceptable methods of contraception)
8. In Part A: Volunteers must be non-smokers for at least 3 months prior to first studyvaccine administration. In Part B: Volunteers may be light smokers i.e. up to a maximum of 5 cigarettes per day or nicotine equivalent.
9. Must be willing to consent to have data entered into The Over Volunteering Prevention System (TOPS).
10. The volunteer's primary care physician has confirmed within the last 12 months that there is nothing in their medical history that would preclude their enrolment into a clinical trial.

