9.2 Exclusion Criteria

1. Volunteers with history or presence of significant cardiovascular disease, pulmonary, hepatic, gallbladder or biliary tract, renal, haematological, gastrointestinal, endocrine, immunologic, dermatological, neurological, psychiatric, autoimmune disease or current infection.
2. Pregnant or lactating females.
3. Laboratory values at screening which are deemed to be clinically significant, unless agreed in advance by the Sponsor's Responsible Medic and Principal Investigator.

4. Current or history of drug or alcohol abuse, or a positive urine drugs of abuse test or alcohol breath test at screening or prior to first dosing (note that a positive drugs of abuse result for a regular medication allowed by this protocol will be permitted).
5. Positive for human immunodeficiency virus (HIV), hepatitis B or hepatitis C.
6. Participation in a clinical drug study during the 90 days preceding the initial dose in this study.
7. Any significant illness during the 4 weeks preceding check-in for this study (Day 1).
8. Volunteers with a history of severe allergic reactions after previous vaccination.
9. Volunteers who have received any vaccine within 30 days of screening, or who are planning to receive a vaccine up to Day 85 of the study.
10. Volunteers receiving immunosuppressive therapy (e.g. systemic steroids, cancer therapies, methotrexate, azathioprine) in the 6 months prior to screening, antibiotics within 10 days of receiving the first dose or taking any short-term medications including over-the-counter preparations, vitamins, herbal and/or mineral supplements within 7 days of the first dose. Chronic medications such as antihypertensives, bronchodilators, oral contraceptives or statins that do not affect the immune system, will be permitted and allowed to continue during the study at the discretion of the Investigator. Paracetamol will be permitted for the treatment of headache or other symptoms.
11. Volunteers with tattoos at the proposed site of vaccine administration.
12. Donation of blood or blood products within 90 days prior to vaccine administration.
13. Volunteers who, in the opinion of the Investigator, are unsuitable for participation in the study.

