10.2 Randomisation

Volunteers will be randomised pre-dose on the morning of Day 1, once all eligibility criteria have been verified. A randomisation list will be held on site, which will be accessible only to unblinded study personnel.

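### Section 6.3 contraindicates GBS-NN in known aluminium hydroxide allergy, but no criterion in the eligibility list verified before randomisation names it

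*Combined protocol and SAP*

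**What the plan says.** Section 6.3 (Risk/Benefit Assessment) describes the adjuvant: "The vaccine is adsorbed with a known adjuvant, Alhydrogel", at 0.5 mg of aluminium per dose. The same section then sets the restriction: "GBS-NN vaccination is contraindicated in volunteers known to suffer hypersensitivity reactions to vaccines or a known allergy to aluminium hydroxide".

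The eligibility lists in 9.1 and 9.2 contain one criterion about allergy, exclusion 8: "Volunteers with a history of severe allergic reactions after previous vaccination". Four general criteria could also bear on an allergic volunteer:

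- Inclusion 1: "Healthy adult female volunteers (as determined by medical history, physical examination, laboratory test values", followed by vital signs and ECG.
- Inclusion 10: the primary care physician has confirmed within 12 months that "there is nothing in their medical history that would preclude their enrolment into a clinical trial".
- Exclusion 1: "Volunteers with history or presence of significant cardiovascular disease, pulmonary, hepatic, gallbladder or biliary tract, renal, haematological, gastrointestinal, endocrine, immunologic, dermatological, neurological", continuing to psychiatric and autoimmune disease and current infection.
- Exclusion 13: "Volunteers who, in the opinion of the Investigator, are unsuitable for participation in the study".

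Section 10.2 places randomisation before dosing on Day 1, "once all eligibility criteria have been verified". Section 12.1 lists medical history among the screening assessments, with no separate allergy item.

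**The concern.** A contraindication protects a volunteer only if someone looks for it before the injection. Here it appears in the risk/benefit narrative, while the list that staff verify before randomising does not mention it. A known allergy is found by asking. The examinations and tests that Sections 12.2.1 and 12.2.2 list for confirming eligibility at Visit 2 (pregnancy test, brief physical examination, drug screen, alcohol breath test) would not reveal it.

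What is at stake is the safety of healthy volunteers given a vaccine that Section 6.3 says has not been tested in humans before. Safeguards after dosing exist but act only once the volunteer has been exposed. They are also lighter in Part B. Section 8.1 requires no sentinel dosing there, and Section 12.2.2 asks for at least 2 hours on site after each dose. For Part A, Section 12.2.1 asks for at least 8 hours after the first dose and 4 after the booster.

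**Working it through.** The plan gives no figure to reproduce. The check compares two parts of the text, then counts exposure for scale.

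**Step 1. Each restriction in Section 6.3 against the eligibility lists.**

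| Restriction in 6.3 | Matching criterion in 9.1 or 9.2 |
|---|---|
| Significant illness in the four weeks before check-in | Exclusion 7 |
| Immune deficiency, autoimmune disease, acute infection | Exclusion 1 (immunologic and autoimmune disease, current infection) |
| Pregnancy, nursing | Exclusion 2 |
| Contraception with pregnancy testing | Inclusion 7 |
| Hypersensitivity to vaccines | Exclusion 8, in part: severe reactions only |
| Known aluminium hydroxide allergy | None that names it |

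The last row is the only one without a named counterpart, and the row above it is matched only in part. Neither eligibility list shows a redaction, so removed text does not explain the absence.

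**Step 2. Whether the general criteria fill the gap.** Inclusion 1 depends on what the medical history brings out. Inclusion 10 is a general statement from the primary care physician. Exclusion 1 requires significant disease and does not mention allergy. Exclusion 13 works once the investigator knows of the allergy. Each gives grounds to exclude, but none names the allergy. A volunteer with a known aluminium hydroxide allergy and no severe reaction to an earlier vaccine meets no named exclusion.

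**Step 3. How many volunteers would receive Alhydrogel.**

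Part A, cohorts 1 to 6 (dose table in 10.1; 8 active and 2 placebo per cohort in 12.2.1):

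- Adjuvanted cohorts: 3, 5 and 6.
- Active: 3 × 8 = 24.
- Placebo: 3 × 2 = 6, which agrees with the 6 Alhydrogel placebo recipients in 15.4.4.
- Total: 24 + 6 = 30 of 6 × 10 = 60, or 50%.

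Optional cohort 7 (10 volunteers, adjuvant undecided): 30 of 70 (43%) if it is unadjuvanted. If it is adjuvanted, 40 of 70 (57%), assuming its placebo also contains Alhydrogel, as in cohorts 3, 5 and 6.

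Part B (10.1 and 12.2.2; up to 60 active volunteers per regimen, three regimens): 10.1 anticipates adjuvanted regimens but leaves the choice open. With 0, 1, 2 or 3 adjuvanted regimens, active recipients number up to 0, 60, 120 or 180. The composition of the Part B placebo cannot be read from the documents, so no placebo count is given.

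Aluminium per recipient: 0.5 mg × at most 2 doses = at most 1.0 mg.

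**The case against.** The strongest reply is that the safeguard already binds. Section 6.3 is protocol text and states the contraindication without qualification. Under Section 16.1 the investigator agrees to follow the protocol. Exclusion 13 gives a direct route to exclude, and a contraindication written in the protocol is an obvious reason to use it. Medical history is taken at screening. All of this stands. A reader might infer that the plan allows an allergic volunteer to be vaccinated; the documents do not support that.

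A reader might also infer that the question goes unasked at the site. That cannot be shown. The medical history form, the eCRF and any site checklist are not in the documents, and they may well include allergies. What can be shown is that nothing in 9.1, 9.2 or 12.1 requires the question.

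Two further extensions are tempting. One is to ask for an exclusion covering every component of the vaccine and placebo. Section 6.3 contraindicates only vaccine hypersensitivity and aluminium hydroxide allergy, so leaving other components unnamed contradicts nothing, and the product description is too heavily redacted to judge the need. The other is to read 6.3 as barring anyone who has ever had any reaction to a vaccine. Its wording concerns volunteers known to suffer such reactions, so the difference from exclusion 8 is real but should not be enlarged.

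What survives is the mismatch itself: the list on which randomisation depends omits one stated contraindication and narrows another.

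**Conclusion.** The point holds as an inconsistency between Section 6.3 and the eligibility criteria, and it is minor. Dosing an allergic volunteer is already contrary to the protocol, and no endpoint, sample size or analysis is affected.

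The counts of 30 of 60 in Part A and up to 180 active recipients in Part B show that Alhydrogel exposure is a substantial part of the study. A reader might take them as numbers at risk of an allergic reaction. They are not: the documents give no prevalence of aluminium hydroxide allergy, so the number of volunteers who could be affected is unknown. The Part B figure also assumes that all three regimens are adjuvanted and filled to their maximum.

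**What to change.** Add an exclusion to 9.2 for known allergy to aluminium hydroxide, and put the matching item on the eligibility checklist. Widen exclusion 8 so that it covers hypersensitivity reactions to vaccines, in line with Section 6.3. The alignment should run in that direction, since limiting 6.3 to severe reactions would weaken a stated safety restriction in a first-in-human study.

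The cost is a small protocol amendment, which needs Ethics Committee review and approval under Section 16.2, plus the checklist item. The new exclusion and the widened exclusion 8 would remove only volunteers for whom Section 6.3 already contraindicates the vaccine.

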7. STUDY OBJECTIVES AND ENDPOINTS

7.1 Primary Objective

The primary objective is to evaluate the safety and tolerability of the GBS-NN vaccine for 12 weeks after the first dose of vaccine.

The following endpoints will be evaluated to support this objective: local and systemic reactogenicity; adverse events; laboratory tests; urinalysis; vital signs; 12-Lead ECG parameters; physical examination.

7.2 Secondary Safety Objectives

The secondary safety objective for Part B is to evaluate the long term safety profile of the GBS-NN vaccine up to 1 year following the first dose.

The same endpoints will be evaluated as for the primary objective.

7.3 Secondary Immunological Objectives

The secondary immunological objectives for both parts of the study are:

- To evaluate IgG antibody responses induced by different vaccine doses alone or in the presence of Alhydrogel over time in healthy female volunteers.
- To determine the impact of pre-existing antibody levels on the vaccine-induced antibody response.

In addition for Part A:

- To determine the effect of Alhydrogel® adjuvant on the immunogenicity of GBS-NN vaccine.
- To select the dose levels and regimens for vaccination of cohorts in Part B, based on the antibody levels at 8 weeks following the first dose (Day 57).

In addition for Part B:

- To evaluate the immune response to the GBS-NN vaccine up to 1 year following the first dose.

The following endpoints will be evaluated by group and time-point to support these objectives:

- Geometric mean antibody concentration in µg/mL.
- Geometric mean fold increase in antibody concentration.
- Seroconversion rate (proportion of volunteers with fold increase above threshold).

8. STUDY DESIGN

8.1 Overview

This is a Phase I, randomised, double-blind, placebo-controlled, parallel group, single centre study.

The study comprises 2 parts. All cohorts in Part A will incorporate sentinel dosing of 2 volunteers in each cohort for the primary dose only: 1 on active treatment and 1 on placebo. No further volunteers in that cohort will be dosed until at least 24 hours after dosing the second volunteer, provided that there are no serious or unexplained safety issues as determined by the Investigator.

In Part A, the decision to proceed with administration of the primary dose in subsequent cohorts will be made as follows:

- Safety will be assessed after at least 7 evaluable volunteers in cohort 1 (sentinel and main) have completed Visit 4 (Day 8), at which point the decision will be made whether to proceed with administration of the primary dose in cohorts 2 and 3.
- Safety will be assessed after at least 7 evaluable volunteers in each of cohorts 2 and 3 have completed Visit 4 (Day 8), at which point the decision will be made whether to proceed with administration of the primary dose in both cohorts 4 and 5 or just one of these cohorts.
- Safety will be assessed after at least 7 evaluable volunteers in each of cohorts 4 and 5 have completed Visit 4 (Day 8), at which point the decision will be made whether to proceed with administration of the primary dose in cohort 6.

In Part B, sentinel dosing is not required, and volunteers in all groups may be randomised and dosed concurrently.

8.2 Study Centre(s)

The study will be performed at a single centre based in the United Kingdom.

8.3 Study Duration

Study start is defined as check-in to the study unit on Day 1. In Part A, each individual volunteer will be involved in the study for approximately 12 weeks (excluding the 28 day screening period and the 6 month safety follow up phone call). In Part B, each individual volunteer will be involved in the study for approximately 1 year (excluding the 28 day screening period).

9. STUDY POPULATION

9.1 Inclusion Criteria

1. Healthy adult female volunteers (as determined by medical history, physical examination, laboratory test values, vital signs and electrocardiograms [ECGs] at screening) aged 18 – 40 years.
2. Body mass index (BMI) ≥ 18 and ≤ 30 kg/m².
3. Volunteers weight ≥ 50 kg and ≤ 100 kg at screening.
4. Able to voluntarily provide written informed consent to participate in the study.
5. Must understand the purposes and risks of the study and agree to follow the restrictions and schedule of procedures as defined in the protocol.
6. Volunteers must be pre-menopausal. Volunteers who have had a hysterectomy will have pre-menopausal status confirmed by a FSH and oestradiol test.
7. Females of childbearing potential must have a negative pregnancy test at screening (β HCG) and prior to each dose and must be willing to use an adequate and highly effective method of contraception until at least Day 85 of the study. A highly effective method of birth control is defined as one which results in a low failure rate (i.e. less than 1% per year) when used consistently and correctly such as sterilisation, implants, injectables, combined oral contraceptives, IUDs (Intrauterine Device), condoms, occlusive caps (cervical/vault caps) with spermicidal foam/gel/ film/cream/suppository. True sexual abstinence is acceptable when this is in line with the preferred and usual lifestyle of the volunteer (periodic abstinence e.g. calendar, ovulation, symptothermal, post-ovulation methods, declaration of abstinence for the duration of the trial, and withdrawal are not acceptable methods of contraception)
8. In Part A: Volunteers must be non-smokers for at least 3 months prior to first studyvaccine administration. In Part B: Volunteers may be light smokers i.e. up to a maximum of 5 cigarettes per day or nicotine equivalent.
9. Must be willing to consent to have data entered into The Over Volunteering Prevention System (TOPS).
10. The volunteer's primary care physician has confirmed within the last 12 months that there is nothing in their medical history that would preclude their enrolment into a clinical trial.

9.2 Exclusion Criteria

1. Volunteers with history or presence of significant cardiovascular disease, pulmonary, hepatic, gallbladder or biliary tract, renal, haematological, gastrointestinal, endocrine, immunologic, dermatological, neurological, psychiatric, autoimmune disease or current infection.
2. Pregnant or lactating females.
3. Laboratory values at screening which are deemed to be clinically significant, unless agreed in advance by the Sponsor's Responsible Medic and Principal Investigator.

4. Current or history of drug or alcohol abuse, or a positive urine drugs of abuse test or alcohol breath test at screening or prior to first dosing (note that a positive drugs of abuse result for a regular medication allowed by this protocol will be permitted).
5. Positive for human immunodeficiency virus (HIV), hepatitis B or hepatitis C.
6. Participation in a clinical drug study during the 90 days preceding the initial dose in this study.
7. Any significant illness during the 4 weeks preceding check-in for this study (Day 1).
8. Volunteers with a history of severe allergic reactions after previous vaccination.
9. Volunteers who have received any vaccine within 30 days of screening, or who are planning to receive a vaccine up to Day 85 of the study.
10. Volunteers receiving immunosuppressive therapy (e.g. systemic steroids, cancer therapies, methotrexate, azathioprine) in the 6 months prior to screening, antibiotics within 10 days of receiving the first dose or taking any short-term medications including over-the-counter preparations, vitamins, herbal and/or mineral supplements within 7 days of the first dose. Chronic medications such as antihypertensives, bronchodilators, oral contraceptives or statins that do not affect the immune system, will be permitted and allowed to continue during the study at the discretion of the Investigator. Paracetamol will be permitted for the treatment of headache or other symptoms.
11. Volunteers with tattoos at the proposed site of vaccine administration.
12. Donation of blood or blood products within 90 days prior to vaccine administration.
13. Volunteers who, in the opinion of the Investigator, are unsuitable for participation in the study.

